## **7.6. Exploratory Omics Analysis**

Various proteomics, transcriptomics, and genomic analyses may be performed on collected data for biomarker exploration. Additional details regarding the statistical methods for these analyses will be described in a separate plan.

## **7.7. Safety Analyses**

### **7.7.1 Adverse Events**

All AEs will be coded using the latest version of the Medical Dictionary for Regulatory Activities. The incidence of TEAEs, organized by system organ class and frequency, will be summarized by seriousness, severity, relationship to treatment, and by treatment at onset of the TEAE. A detailed listing of serious AEs and TEAEs leading to withdrawal will also be provided.

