### **5.1.2 Dosing Schedule**

- Treatment Group A: Avonex 7.5 µg, IM
- Treatment Group B: Avonex 15 µg, IM
- Treatment Group C: Avonex 30 µg, IM
- Treatment Group D: Plegridy 31.25 µg, SC
- Treatment Group E: Plegridy 62.5 µg, SC
- Treatment Group F: Plegridy 125 µg, SC
- Treatment Group G: Placebo (6 subjects receive IM and 6 subjects receive SC)

Subjects randomized to Treatment Groups A-C will be discharged on Day 7, while subjects randomized to Treatment Groups D-G will be discharged on Day 14. If a subject discontinues from the study prematurely, all procedures scheduled for discharge Day (i.e., Day 7 or Day 14) will be performed.

Safety will be evaluated in terms of AEs, clinical laboratory results (hematology, serum chemistry, and urinalysis), vital sign measurements (blood pressure, heart rate, respiratory rate, and oral body temperature), safety ECG results, and physical examination findings (see Table 9-1).

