### **5.6.3 Study Periods**

This is a randomized, placebo-controlled, single-dose, parallel arm study. Healthy subjects will be randomized to three dose groups (low, intermediate, and high) of each drug (Avonex or Plegridy) or placebo. Subjects randomized to the Avonex Treatment Groups (A-C) will be discharged on Day 7, while subjects randomized to the Plegridy or placebo Treatment Groups (D-G) will be discharged on Day 14.

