#### **5.7.4.1 Adverse Events**

##### **5.7.4.1.1 Adverse Event Definitions**

An AE is defined as any untoward and/or unintended sign, including an abnormal clinical laboratory finding, symptom, or disease temporally associated with the use of a study drug, whether or not considered related to the study drug. Events or conditions that increase in frequency or severity during or as a consequence of use of a drug in human clinical trials will also be considered AEs.

A treatment-emergent adverse event (TEAE) is defined as an AE that begins after study drug administration.

An unexpected AE is any AE having a specificity or severity not consistent with the current investigator's brochure for the study drug(s).

An SAE is defined as any AE occurring at any dose that meets the following criteria:

- Results in death,
- Is life threatening,

- Requires hospitalization or prolongation of existing hospitalization,
- Results in persistent or significant disability or incapacity,
- Is a congenital anomaly/birth defect, or
- Is an important medical event that may not meet the previous criteria but, based upon appropriate medical judgment, jeopardizes the subject or requires medical or surgical intervention to prevent one of the outcomes listed previously.

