#### **5.7.4.1.2 Adverse Event Reporting**

The recording of AEs will begin after the subject signs the informed consent form and will continue until discharge (or early termination). All AEs, whether serious or nonserious and whether or not related to the study drug, must be recorded in the eCRF. Study subjects will be instructed to warn study staff if he or she has any unexpected symptoms. In addition, all subjects will receive a reminder telephone call approximately 24 hours before Check-in.

Any SAE (whether expected or unexpected) must be entered into the eCRF system and reported by facsimile to the medical monitor or designee using the SAE Reporting Form within 24 hours of the investigator or study clinic staff becoming aware of the event. It is the responsibility of the investigator to report all SAEs to the medical monitor, to provide the most complete report possible, and to assess each SAE for its relationship to the study drug. The investigator is responsible for obtaining follow-up information on all SAEs and submitting follow-up SAE data. Any unexpected SAEs must be reported promptly to the investigator's IRB as per the IRB's requirements.

In the event of a fatal or life-threatening SAE, the sponsor will notify the appropriate FDA authorities by telephone or facsimile within 7 calendar days of receipt of the report. The sponsor will follow all 7-day alert reports with a written report within 10 working days of receipt of the case. Serious AE cases that concern nonfatal, nonlife-threatening events that are unexpected and at least possibly related to the study drug will be submitted in writing to the FDA within 10 working days of receipt.

Furthermore, any AEs that are not expected, occur at a higher frequency, or would require modification of the study protocol and/or informed consent must be reported to the FDA within 10 working days.

Adverse events that are assessed by the investigator as possibly or probably related to the study drug will be followed until they resolve or stabilize. All SAEs will be followed until resolution.

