## **3. Study Overview**

### **3.1. Study Design**

This is a randomized, double-blind, placebo-controlled, single-dose, parallel arm, pilot study. Healthy subjects will be randomized to one of three dose groups (low, intermediate, and high) for each drug (IFN  $\beta$ -1a and pegIFN  $\beta$ -1a) or placebo (See Table 1). The study will be conducted at one center in the United States (Spaulding Clinical Research unit in West Bend, Wisconsin).

Subjects randomized to Treatment Groups A, B, and C will stay in-house for the duration of the study and will be discharged on Day 7. Subjects randomized to Treatment Groups D, E, F, and G will stay-in house until Day 10 and return for the Day 14 assessment. Each treatment group should include equal representation of male and female subjects.

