#### **7.7.4 Safety 12-lead Electrocardiograms**

The incidence of pathological ECG interpretive statements at Baseline and during treatment will be assessed among the treatments.

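### TEAE incidence is tabulated by treatment with no common window, although Avonex is followed to Day 7 and placebo and Plegridy to Day 14

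*SAP*

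**What the plan says.** The AE summary in SAP 7.7.1 reads: "The incidence of TEAEs, organized by system organ class and frequency, will be summarized by seriousness, severity, relationship to treatment", followed by treatment at onset. Protocol 5.9.8.1 has the same text. In a single-dose parallel study each subject has only one treatment, so splitting by treatment at onset does not separate early events from late ones.

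Three other places fix the length of observation:

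- Protocol 5.7.4.1.2: "The recording of AEs will begin after the subject signs the informed consent form and will continue until discharge (or early termination".
- Protocol 5.1.2, with 5.1 and 5.6.3 in agreement: "Treatment Groups A-C will be discharged on Day 7, while subjects randomized to Treatment Groups D-G will be discharged on Day 14".
- Protocol 5.7.4.1.1: "A treatment-emergent adverse event (TEAE) is defined as an AE that begins after study drug administration". The definition has no closing day.

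SAP 3.1 describes the longer arms differently: "Treatment Groups D, E, F, and G will stay-in house until Day 10 and return for the Day 14 assessment". Neither document says how adverse events between Day 10 and Day 14 are captured under that schedule.

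Vital signs, by contrast, are summarised by treatment and time point (protocol 5.9.8.3, SAP 7.7.3), so those tables can be read on matched days.

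**The concern.** An incidence is the share of subjects with at least one event during the time they are watched. Here that time depends on the arm. Placebo subjects can contribute background events, such as headache, for a further week after the Avonex subjects have gone home. A placebo column is normally read as the background against which the active columns are judged. The three Avonex columns would be judged against a background collected over a longer period. They would also be set beside Plegridy columns collected over that longer period. Plegridy against placebo is not affected, because both end on the same day.

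What is at stake is how the tolerability of three Avonex doses in healthy volunteers is read. With 12 subjects per arm, one subject is 8.3 percentage points (1/12), so one or two placebo subjects whose first event comes after Day 7 would visibly change the table.

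**Working it through.** **Inputs from the documents.** Observation ends on Day 7 for A-C and Day 14 for D-G (protocol 5.1.2), or Day 10 for D-G if only the SAP 3.1 in-house stay is counted. Each arm has 12 subjects (protocol Table 5-1). No adverse-event rate is given, so there is no figure of the plan's own to reproduce.

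**Observation time.** Placebo to Avonex is 14/7 = 2.0 in calendar days, or 12 × 14 = 168 against 12 × 7 = 84 person-days per arm. Counted from dosing on Day 1, it is 13/6 = 2.17. On the SAP in-house stay alone, it is 10/7 = 1.43, or 9/6 = 1.5 from dosing.

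**Direction, without a model.** Placebo subjects with an event by Day 14 include every placebo subject with one by Day 7. The whole-stay placebo incidence therefore cannot be below the Day 7 incidence, and the crude Avonex-minus-placebo difference cannot exceed the matched-window difference. The same argument applies to Plegridy. It holds in the realised data for any kind of event counted as subjects with at least one.

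**Size, under assumptions.** Let p7 be the 7-day background risk, assumed to lie between 5% and 50%. The shortfall in the crude difference is the placebo risk over the longer period minus p7.

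- Constant hazard to Day 14: risk = 1 − (1 − p7)^(14/7). For p7 = 20%: 1 − 0.80² = 36%, a shortfall of 16 points.
- Constant hazard, events recorded to Day 10 only: risk = 1 − (1 − p7)^(10/7).
- A share s of the placebo hazard falls after Day 7: risk = 1 − (1 − p7)^(1/(1 − s)). A constant hazard is s = 50%.

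Shortfall in percentage points:

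| Assumed p7 | Constant, to Day 14 | Constant, to Day 10 | s = 25% | s = 10% | s = 0 |
|---|---|---|---|---|---|
| 5% | 4.8 | 2.1 | 1.6 | 0.5 | 0 |
| 10% | 9.0 | 4.0 | 3.1 | 1.0 | 0 |
| 20% | 16.0 | 7.3 | 5.7 | 2.0 | 0 |
| 30% | 21.0 | 9.9 | 7.8 | 2.7 | 0 |
| 50% | 25.0 | 12.9 | 10.3 | 3.7 | 0 |

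**One illustration.** Take a 20% background and a 30% attributable Avonex risk. Avonex incidence is 1 − 0.80 × 0.70 = 44%. In a common 7-day window the difference is 44 − 20 = 24 points (risk ratio 2.20). The crude table under a constant hazard shows 44 − 36 = 8 points (risk ratio 1.22). With only 10% of the hazard after Day 7, it shows 44 − 22 = 22 points.

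**After the fix.** With a common Day 1 to 7 window, observation is 84 against 84 person-days and the shortfall is zero whatever the hazard.

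**The case against.** The strongest reply is that no biased quantity is planned. No endpoint in either document concerns safety, the AE tables are descriptive, and no Avonex-placebo risk difference or test is defined. That stands: the problem enters only when someone reads the columns against each other. But a by-treatment table in a placebo-controlled study invites that reading, and nothing warns the reader that the columns cover different periods.

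Second, there is mitigation. TEAEs are also split by relationship to treatment, on a scale that considers timing relative to dosing (protocol 5.7.4.1.4), and all data are listed. Late background events can therefore be partly separated, and a Day 7 cut can be made afterwards. This limits the harm, but it leaves the overall incidence as it is and the choice of window to be made after the data are seen.

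Third, a constant hazard may be too harsh. There is one injection, on Day 1, so its local effects need not continue into the second week. Venipuncture does not double either: SAP Attachment A has 14 PK sampling times through Day 7 and 4 more for D-G, a ratio of 18/14 = 1.29. If the hazard followed that ratio, a 7-day risk of 30% would become about 37%, not 51%, and 20% would become about 25%, not 36%. This also stands, which is why the size is given as a range that includes zero.

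Two stronger readings are tempting:

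- **The table would reverse the sign of a real Avonex excess.** With 50% on Avonex and a 30% seven-day background, a constant hazard gives 50% against 51%. With the sampling-time ratio, the same inputs give about 50% against 37%. The reversal comes from the chosen inputs, and the documents supply none.
- **The ECG summary in SAP 7.7.4 has the same fault.** It says: "The incidence of pathological ECG interpretive statements at Baseline and during treatment will be assessed among the treatments". The schedule of events (Table 9-1) is not available in the text reviewed, so it cannot be shown that placebo subjects have more post-dose ECGs than Avonex subjects. Every arm has a discharge ECG (protocol 5.6.4), and protocol 5.9.8.4 also summarises ECG data by time point.

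**Conclusion.** The point holds for adverse events only. As written, SAP 7.7.1 sets 7-day Avonex incidences beside placebo and Plegridy incidences collected over 14 days, or over 10 if only the SAP in-house stay counts. The direction is certain: Avonex relative to placebo is either unchanged or understated, and Avonex is favoured beside Plegridy.

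The size cannot be taken from the documents. It runs from zero, if no placebo hazard falls after Day 7, up to 25 points at a 50% seven-day risk with a constant hazard. It rests on the assumed background risk and on how that risk is spread over the two weeks. Events clustered in the first days would produce little distortion, and steady background complaints would produce more. The tables are descriptive and the data remain available, so this is a presentation fault worth correcting before the tables are produced. It is not a flaw in a planned inference.

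**What to change.** In SAP 7.7.1:

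- Tabulate TEAEs with onset from dosing through Day 7 in all seven arms, and use this table for any reading of Avonex against placebo or Plegridy.
- Tabulate TEAEs through Day 14 for D-G only, for Plegridy against placebo.
- If a whole-stay table of all arms is kept, print person-days for each arm beside the incidences and state the two follow-up lengths in a footnote.

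Separately, reconcile SAP 3.1 with protocol 5.1, 5.1.2 and 5.6.3 on where groups D-G are between Day 10 and Day 14, and state whether and how adverse events in that interval are recorded. Until that is settled, the Day 14 table has no clear observation period.

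The cost is one extra cut of existing AE data. Whether an event is treatment-emergent already depends on when it began, so no new data collection is needed.

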### **7.7.2 Clinical Laboratory Tests**

Clinical laboratory results (hematology, serum chemistry, and urinalysis) will be summarized using descriptive statistics (number of subjects, mean, SD, minimum, median, and maximum). Clinical laboratory results will be classified as normal or abnormal, according to the reference ranges of the individual parameter. No statistical testing will be performed on clinical laboratory data.

### **7.7.3 Vital Sign Measurements**

Vital sign measurements and changes from Baseline will be summarized using descriptive statistics (number of subjects, mean, SD, minimum, median, and maximum) by treatment and time point.

#### **7.7.4 Safety 12-lead Electrocardiograms**

The incidence of pathological ECG interpretive statements at Baseline and during treatment will be assessed among the treatments.

#### **7.7.5 Physical Examinations**

Physical examination findings will be presented in a data listing, and abnormal physical examination findings will be recorded as AEs.

#### **7.7.6 Other Safety Data**

All concomitant medication usage and medications that changed in daily dose, frequency, or both since the subject provided informed consent will be summarized for each subject.

### **8. Data Quality Assurance**

Completed eCRFs are required for each subject randomized to study drug. Electronic data entry will be accomplished through the ClinSpark® remote electronic data capture system, which allows for on-site data entry and data management. This system provides immediate, direct data transfer to the database, as well as immediate detection of discrepancies, enabling site coordinators to resolve and manage discrepancies in a timely manner. Each person involved with the study will have an individual identification code and password that allows for record traceability. Thus, the system, and subsequently any investigative reviews, can identify coordinators, investigators, and individuals who have entered or modified records.

Furthermore, the investigator retains full responsibility for the accuracy and authenticity of all data entered into the electronic data capture system.

## **Attachment A. Pharmacokinetic, Pharmacodynamic, and Biomarker Sample Collection Schedule**

### **Pharmacokinetic Sample Collection**

Pharmacokinetic blood samples (5 mL) for determination of IFN  $\beta$ -1a and pegIFN  $\beta$ -1a concentration will be collected at the following time points:

- Day 1: 0 (pre-dose), 1, 3, 6, 8, 16 h
- Day 2: 24, 32, 40 h
- Day 3, 4, 5, 6, 7
- Day 8, 9, 10, and 14 (Arms D, E, F, and G, only)

Blood samples will be collected by direct venipuncture or by inserting an IV catheter into the subject's forearm region. Each blood sample will be labeled with subject number, study number, study day, time point, event, and a barcode that matches that belonging to the subject.

### **Pharmacodynamic Sample Collection**

Blood samples for primary pharmacodynamic biomarker (neopterin, 5 mL) and secondary pharmacodynamic biomarker (MxA, 1 mL) assessments will be collected at the following time points:

- Screening (Day -21 to -2)
- Day 1: 0 (pre-dose), 1, 3, 6, 8, 16 h
- Day 2: 24, 32, 40 h
- Day 3, 4, 5, 6, 7
- Day 8, 9, 10, and 14 (Arms D, E, F, and G, only)

Blood samples will be collected by direct venipuncture or by inserting an IV catheter into the subject's forearm region. Each blood sample will be labeled with subject number, study number, study day, time point, event, and a barcode that matches that belonging to the subject.

### **Exploratory PD Biomarkers**

Exploratory PD biomarkers will be evaluated using plasma proteomics and small RNA transcriptomics. Whole blood samples (5 mL) will be collected and processed for plasma at the following time points:

- Day 1: 0 (pre-dose), 1, 3, 6, 8, 16, 24 h
- Day 2: 24, 32, 40 h

- Day 3, 4, 5, 6, 7
- Day 8, 9, 10, and 14 (Arms D, E, F, and G, only)

Blood samples will be collected by direct venipuncture or by inserting an IV catheter into the subject's forearm region. Each blood sample will be labeled with subject number, study number, study day, time point, event, and a barcode that matches that belonging to the subject. All blood samples will be processed for preparation of plasma.

## Attachment B. Randomization Schedule

Subjects will enter the study clinic for check-in procedures the day before study drug administration of the first period (Day -1). IFN  $\beta$ -1a will be administered intramuscularly and pegIFN  $\beta$ -1a will be administered subcutaneously. Placebo will be administered either subcutaneously or intramuscularly to match study drug. On Day 1, subjects will receive their assigned treatment according to the randomization schedule generated by the randomization biostatistician (unblinded and unaffiliated with study data analysis) and provided to designated unblinded recipients (i.e., pharmacist) at the clinical site.

Treatment Group	Drug
A	Interferon beta-1a (Avonex®) low (7.5 $\mu$ g)
B	Interferon beta-1a (Avonex®) intermediate (15 $\mu$ g)
C	Interferon beta-1a (Avonex®) high (30 $\mu$ g)
D	Peginterferon beta-1a (Plegridy®) low (31.25 $\mu$ g)
E	Peginterferon beta-1a (Plegridy®) intermediate (62.5 $\mu$ g)
F	Peginterferon beta-1a (Plegridy®) high (125 $\mu$ g)
G	Placebo
